5. VARIABLES AND THEIR ASSESSMENT

5.1 TRIAL ENDPOINTS

5.1.1 Primary Endpoint(s)

The primary efficacy endpoint is the proportion of patients with complete renal response at week 52.

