7.5 HANDLING OF MISSING DATA

As an imputation technique to deal with the missing data in this study, for the analysis of primary and secondary endpoints, non-completers considered failure (NCF) will be used. All other endpoints will be analysed without imputing for any missing data.

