Definition/derivation of CRR for patients who prematurely stop trial medication

The rules below will be applied to derive CRR/PRR/MRR for the ITT:

Proprietary confidential information © 2020 Boehringer Ingelheim International GmbH or one or more of its affiliated companies

- (1) If the reason for discontinuation of treatment is ‘Lack of efficacy’ or AE type is ‘Worsening of disease under study’, then CRR will be defined as ‘Non-responder’.
- (2) If the patient used prohibited meds known to impact CRR following discontinuation of study med, then CRR will be defined as ‘Non-responder’.
- (3) If neither #1 or #2 apply and treatment duration ≥ 46 weeks, then use the lab data collected at Visit 16-EOT/Week 52 to derive the endpoints. If there is no lab data at Visit 16-EOT /Week 52, then use the lab data closest to 52 weeks that is within 6 weeks prior to week 52.
- (4) If neither #1 or #2 apply and treatment duration < 46 weeks, then CRR will be defined as ‘Non-responder’.

Note that patients handled with the above rules are included in the ITT population. They would only be included in the PPS if they complete 46 weeks of the treatment regimen.

For patients who took study drug for < 46 weeks, continued to participate in the trial and have urine collections and serum creatinine determinations, their data will be displayed in a listing.

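### SAP 6.6.1 rule 3 makes no exception for death or trial exit, so a patient who dies, or leaves without end-of-treatment labs, after 46 weeks on drug can be scored a week-52 complete responder

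*SAP*

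**What the plan says.** The primary endpoint is "the proportion of patients with complete renal response at week 52" (Protocol 5.1.1). Protocol 7.5 gives one missing-data rule: "for the analysis of primary and secondary endpoints, non-completers considered failure (NCF) will be used". It makes no exception for late stops.

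SAP 6.6.1 replaces this with four ordered rules for patients who stop trial medication prematurely:

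- **Rule 1:** a stop for lack of efficacy, or with an adverse event typed as worsening of the disease under study, is non-response.
- **Rule 2:** "If the patient used prohibited meds known to impact CRR following discontinuation of study med", the result is non-response.
- **Rule 3:** if neither applies and treatment lasted at least 46 weeks, "then use the lab data collected at Visit 16-EOT/Week 52 to derive the endpoints". If those labs do not exist, "then use the lab data closest to 52 weeks that is within 6 weeks prior to week 52".
- **Rule 4:** "If neither #1 or #2 apply and treatment duration < 46 weeks, then CRR will be defined as" non-response.

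SAP 5.1 says that section 6.6.1 also covers patients who left the trial, so exits are in scope. Neither death nor exit is named in any of the four rules. SAP section 4, as far as it is readable, lists other changes from the protocol (the UP/UC derivations, the revised MRR definition, the added covariate) but not this one.

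**The concern.** A patient who has died, or who has left with no assessment near week 52, has no renal response at week 52 to observe. Rule 3 can nevertheless record one, from labs taken while the patient was still alive and in the trial. The order of the rules makes this odd. A living patient who stops at week 45 fails automatically under rule 4, whereas a patient who stops at week 48 and then dies of infection can be a responder.

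The error runs one way, because it can only turn a protocol failure into a response. If late deaths and exits were more frequent in one arm, that arm would gain. The per-protocol set is not an obvious check, since SAP 6.3 admits patients once they have completed 46 weeks of the regimen.

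**Working it through.** **1. The rules applied to cases.** Each patient has qualifying labs at the last assessment.

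| Case | Rule that decides | SAP result | Protocol 7.5, ordinary reading |
|---|---|---|---|
| Last dose week 48, dies of infection week 49, no EOT visit | 3, look-back to week 46 | Responder | Failure |
| Stops week 47, EOT labs week 48, dies of infection week 49 | 3, EOT labs | Responder | Failure |
| Leaves the trial at week 48, no EOT visit | 3, look-back to week 46 | Responder | Failure |
| Dies week 49, event typed as disease worsening | 1 | Non-responder | Failure |
| Stops week 45 | 4 | Non-responder | Failure |

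The second case is possible because Protocol 6.2.3.1 places the EOT visit within 7 days of the last dose, which can be before week 52. Both branches of rule 3 therefore have the gap.

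**2. How many patients.** The documents give no dropout rate. Assume that 10-25% of 120 patients stop early (12-30), evenly over 52 weeks. The share stopping in weeks 46-52 is 6/52 = 11.5%.

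- 12 × 0.115 = 1.4; 30 × 0.115 = 3.5 late stops over all four arms.
- With assumed response rates of 25-45% (Protocol 7.3.1 and 7.7): 1.4 × 0.25 = 0.35; 3.5 × 0.45 = 1.6 with a favourable result.
- Misclassification also needs a death, or an exit without EOT or week-52 labs, so the expected number is lower again.

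**3. What one patient is worth.** 1/40 = 2.5 points (placebo or 240 mg); 1/20 = 5 points (120 or 180 mg). The criterion in Protocol 7.3.1 is a modelled benefit of at least 10 points.

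**4. Effect on the success criterion.** Protocol Table 7.7:1 states 82% success for scenario Expected A (0.25, 0.30, 0.38, 0.44; 40:20:20:40; one-sided 20%). The readable text omits the candidate-model parameters, so three sets were assumed. A simulation of the MCPMod procedure (3,000 runs) gave 82.5%, 83.4% and 81.2%, each within 2 points of the stated figure. The next two checks use the first set.

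- *Late exits equal in all arms* (assumed 1-5% of each arm, 25-100% of them scored as responders; 1,500 runs). Success was 79.9-83.2% under NCF and 78.4-83.1% under rule 3. The largest gap was 79.9 − 78.4 = 1.5 points. Simulation error is about 1 point per estimate, so this cannot be told from zero.
- *All the excess in the 240 mg arm*, with a true flat rate of 25%. False success was about 18-19%. Raising the 240 mg rate by 2.5, 5 or 7.5 points (1, 2 or 3 patients in 40) took it to about 25%, 33% and 42%. This shows sensitivity to imbalance; it is not a forecast.

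**The case against.** The strongest reply is that rule 3 is a reasonable elaboration of a one-line protocol rule. Protocol 7.5 does not define a non-completer and mentions neither death nor exit. Protocol 7.3.1 separately makes patients withdrawn for non-response non-responders, which would be redundant if every drug stopper failed anyway. Protocol 3.3.4.1 stresses recording renal function to week 52 after drug is stopped. The SAP could take 46 weeks of treatment as near enough to completion in an exploratory trial. This has force for a patient who stops late, is alive and has EOT labs. It has none for a patient who has died or left unassessed, who is a non-completer on any ordinary reading.

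Four stronger readings are tempting, and the documents do not support them:

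- **That all late stoppers are scored on labs up to six weeks old.** EOT/Week 52 labs come first and the look-back is a fallback. Protocol 6.2.3.1 asks every early stopper to attend an EOT visit with two 24h collections, and 6.2.3.3 invites them to a week-52 visit.
- **That the six-week limit excludes part of the week-46 visit window.** Read as exactly 42 days, it starts at day 365 − 42 = 323, and 5 of the 11 permitted days (318-328) fall before it. But SAP 6.6.1 elsewhere substitutes week 46 for week 52 by nominal visit, and 52 − 46 = 6. On that reading nothing is excluded. The wording is ambiguous, not shown to be wrong.
- **That the primary result is materially biased.** The expected number is about one patient or fewer, and an equal spread over arms changes almost nothing.
- **That no safeguard exists.** SAP 7.4.2, on sensitivity analyses, has no readable content, so a strict-NCF analysis cannot be ruled out. It would not correct the primary derivation.

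**Conclusion.** The point stands, at modest size. As written, rule 3 can make a week-52 complete responder of a patient who died before week 52 from a cause that rule 1 does not catch, or who left with no EOT or week-52 labs. That departs from Protocol 7.5, and the readable SAP section 4 does not say so.

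The number affected is probably about one patient or fewer. That rests on an assumed 10-25% early-stop rate spread evenly over the year and on the planning response rates. The consequence depends on where such patients fall: negligible if spread over the arms, but a quarter (2.5 points) or a half (5 points) of the 10-point criterion for one patient in one arm. The criterion applies to the modelled benefit, so an observed shift need not carry over one for one. The correction is worth making because it removes a wrong classification at almost no cost.

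**What to change.** Put two statements ahead of rule 3 in SAP 6.6.1:

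- (a) Death before the week-52 assessment is non-response, whatever earlier EOT labs show.
- (b) Trial exit before week 52 with no Visit 16-EOT/Week 52 labs is non-response.

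Part (a) has to cover the EOT branch as well as the look-back; a rule limited to patients without labs would miss the second case in the table. Keep the look-back only for patients alive and still in the trial, and word its source as *the week-46 visit or later*, which removes the day-count ambiguity.

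Scoring late stoppers on EOT labs would remain a departure from NCF. Declare it in SAP section 4, and report a sensitivity analysis under strict NCF unless one is already planned.

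The cost is a few sentences and at most one extra analysis. No new data are needed: reasons for withdrawal go into the eCRF (Protocol 3.3.4.1), and vital status is sought for patients who leave early (flow chart footnote 12 and Protocol 6.2.3.3). The downside is that possibly one or two late exits with good labs become non-responders.

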6.6.2 Other endpoints and safety endpoints

Missing or incomplete AE dates are imputed according to BI standards (see “Handling of missing and incomplete AE dates”). (2)

All other endpoints will be analysed without imputing for any missing data.

6.7 BASELINE, TIME WINDOWS AND CALCULATED VISITS

Study day will be calculated relative to the date and time of the first dose of double-blind randomised treatment. The day prior to the start of double-blind randomised treatment will be ‘Day -1’ and the day of the start of double-blind randomised treatment will be ‘Day 1’; therefore ‘Day 0’ will not exist.

Unless otherwise specified, baseline is defined as the latest time-point on or before the date of the first randomised treatment administration (the date of the first dose is acceptable because the first dose of medication is to be taken in clinic on the day of randomisation AFTER all

Proprietary confidential information © 2020 Boehringer Ingelheim International GmbH or one or more of its affiliated companies

baseline assessments have been made.) If there is no measurement for a particular variable on or before the date of first randomised treatment administration then no baseline will be derived for that variable.

The following visit labels will be used in all tables & graphics. As specified in the CTP, EOT refers to the End of Treatment visit. EOS is the End of Study visit. FU is Follow Up.

For discontinued patients (only):

EOT = 'EOT'

For completed patients who do not roll over to trial 1293.13:

Week 52='Week 52/ EOT'

Week 56='FU'

Week 60='EOS'

For completed patients who roll over to trial 1293.13:

Week 52='Week 52/ EOT'

For patients who discontinue trial drug but continue participation in trial:

EOT='EOT'

Visit 5='Visit 5/FU'

Visit 8='Visit 8/FU'

Visit 11='Visit 11/FU'

Visit 14='Visit 14/FU'

EOS ='EOS/FU'

Visit labels containing 'Visit' or 'FU' occurred after the EOT visit; patient was not on drug for these visits.

7. PLANNED ANALYSIS

For End-Of-Text (EoT) tables, the set of summary statistics is: N / Mean / SD / Min / Median / Max.

For tables that are provided for endpoints with some extreme data, median, quartiles and percentiles should be preferred to mean, standard deviation, minimum and maximum.

Tabulations of frequencies for categorical data will include all possible categories and will display the number of observations in a category as well as the percentage (%) relative to the respective treatment group (unless otherwise specified, all patients in the respective patient set whether they have non-missing values or not). Percentages will be rounded to one decimal place. The category missing will be displayed only if there are actually missing values.

All calculated statistics will be presented to one more decimal place than the original measurement accuracy of the variable being summarised.

All p-values will be displayed to four decimal places (or “<0.0001” if appropriate).

7.1 DEMOGRAPHIC AND OTHER BASELINE CHARACTERISTICS

Only descriptive statistics are planned for this section of the report. The display will include the following variables: gender, ethnicity, race, age, time since diagnosis (months), height, weight, smoking status, alcohol status, LN class, activity score and anti-dsDNA, C3 and C4 at baseline, eGFR at baseline, UP/UC from the spot urine at baseline, UP from the 24h collection at baseline and UP/UC from the 24h collection at baseline.

7.2 CONCOMITANT DISEASES AND MEDICATION

Concomitant disease and medications will be summarized. Frequency counts are planned.

Concomitant diseases will be coded using the current version of MedDRA coding system.

Medications will be coded using the WHO Drug dictionary (WHO-DD). The coding version number will be displayed as a footnote in the respective output.

In addition to the standard display showing all concomitant medications, separate displays will be provided to characterize usage of ACEi (Angiotensin-converting enzyme inhibitors) and ARB (Angiotensin receptor blockers) by treatment group. As usage of these meds may impact renal response, it is of interest to capture the number of patients who use these meds at:

- Baseline
- On-treatment
- At week 52 (when patient is evaluated for the primary endpoint)
- And to capture patients who had any change during the trial (i.e., patients who start use of these meds and who increase or reduce doses). This last group, may be determined programmatically or from manual review using a spreadsheet to identify patients.

Proprietary confidential information © 2020 Boehringer Ingelheim International GmbH or one or more of its affiliated companies

Concomitant diagnoses and medications will be listed by patient. Subjects without any concomitant diagnosis or therapy should be marked with a “No” in the respective column.

7.3 TREATMENT COMPLIANCE

Only descriptive statistics are planned for this section of the report.

7.4 PRIMARY ENDPOINT

7.4.1 Primary analysis of the primary endpoint

Primary analyses of the primary endpoint will be performed using the ITT patient set.

The Multiple Comparison Procedures and Modeling (MCP-Mod) approach (4, 5) is implemented in two main steps: (1) trial design stage; (2) trial analysis stage. The procedures for the trial design stage, including the selection of candidate models covering a suitable range of dose-response shapes and sample size and power calculations, are provided in the CTP Section 7.3.1 and 7.7. The procedures for the trial analysis stage are outlined below with more specification (including SAS code & R code) in [Section 9.1](#).

CRR at week 52 (derived using UP and derived using UP/UC from the 24h urine collections) will be analysed using a logistic regression model. Factors in the model will include treatment and the covariates: race (Asian/non-Asian) and proteinuria at screening $<3\text{g/day}$ or $\geq 3\text{g/day}$ (respectively $U_{\text{prot}}/U_{\text{creat}} < 3$ or $U_{\text{prot}}/U_{\text{creat}} \geq 3$). Use of proteinuria at screening as a covariate was not specified in the CTP. It was added via the TSAP as both race and proteinuria were stratification variables at randomization.

From this model, placebo-adjusted treatment estimates for each active dose group, as well as their corresponding variance-covariance matrix will be estimated. These results will be used in the MCPmod analysis.

Pairwise comparisons of the *modelled proportion* of patients at each dose level who are CRRs will be compared to placebo. In keeping with the exploratory nature of the trial, p-values will be interpreted in a nominal fashion (no adjustment for multiplicity will be performed). While the interim TSAP specified that an alpha level of 0.10 (two-sided) would be the cut-off for declaring statistical significance, this was changed via the Decision log prior to conducting the interim analysis. For consistency with a team-reviewed relevant external publication it was decided that an alpha level of < 0.20 (two-sided) would be the cut-off for declaring statistical significance.

Pairwise comparisons of the *observed* proportions of patients at each dose level to placebo who are CRRs will be performed. Confidence intervals will be calculated using the Newcombe method. P-values from Barnard tests of association will be displayed.

Pairwise comparisons of *stratified observed* proportions of patients at each dose level to placebo who are CRRs will be performed. Confidence intervals will be calculated using the Cochran-Mantel-Haenszel (CMH) method. A single p-value from a CMH test of general association will be displayed.

Proprietary confidential information © 2020 Boehringer Ingelheim International GmbH or one or more of its affiliated companies

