7.2 NULL AND ALTERNATIVE HYPOTHESES

The primary endpoint is proportion of patients with complete renal response at week 52. The null hypothesis is that there is a flat dose response curve looking at the proportion of patients with complete renal response at week 52 in the placebo and the three BI 655064 dosage groups. The alternative hypothesis is that there is a non-flat dose response curve. Additionally it will be investigated whether at least one dose shows a modelled absolute benefit compared to placebo of at least 10%.

The MCPMod procedure allows for the simultaneous evaluation of different potential dose response patterns, whilst protecting the overall probability of type I error of 20%. The pre-specified models and their parameters used for this test are outlined in [Section 7.3.1](#) and [Section 7.7](#).

This is an exploratory trial and no formal statistical testing will be performed. Any p-values or confidence intervals provided are to be interpreted in an exploratory sense.

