7.3.1 Primary endpoint analyses

The primary endpoint is the proportion of patients with complete renal response after 52 weeks of treatment. Patients withdrawn due to non-response are considered non-responders for the analyses at 52 weeks.

The analyses for PoC and dose-finding will be performed using MCPMod techniques ([R10-1424](#), [R15-1961](#)) for binary data whereby several possible dose response models (patterns) will be evaluated (while keeping full control of the type I error) to identify the best-fitting model or subset of models. Due to the rareness of the disease and in order to have a feasible resulting sample size the global α -level has been chosen to be 20% one-sided.

A non-flat dose-response relationship is established if the null hypothesis of no dose effect (i.e. a flat dose response curve) is rejected for at least one of the pre-specified models with respect to the global alpha chosen.

For the sample size calculation, the maximum effect size is assumed to be 45% with the placebo effect size assumed to be 25%. Further details are given in [Section 7.7](#).

The following models shapes have been selected as the candidate set of possible dose response patterns:

Emax : $E_0 + E_{max} * d / (ED_{50} + d)$

Exponential : $E_0 + E_1 * (\exp(d/\delta) - 1)$

Quadratic : $E_0 + \beta_1 * d + \beta_2 * d^2$

Sigmoid Emax : $E_0 + E_{max} * d^h / (ED_{50}^h + d^h)$ Model shapes are illustrated in figure [7-3-1: 1](#). Note that the actual shapes are applied on the parameter scale (logit for binary data) according to Pinheiro et al. ([R15-4293](#)).

[figure not shown]

Figure 7.3.1 : 1: Shape of the models within the candidate set

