4. CHANGES IN THE PLANNED ANALYSIS OF THE STUDY

The primary endpoint, Complete Renal Response (CRR), as defined in the CTP, is derived from urine protein (UP) determined from the 24-hour (24h) urine collections and eGFR calculated from serum creatinine. To account for incomplete 24h collections, an alternate derivation of CRR is added with this version of the TSAP. The alternate derivation is based on the ratio of urine protein/urine creatinine (UP/UC) determined from the 24h collections and eGFR calculated from serum creatinine. This alternate derivation will be analysed and presented using the same methods/format used for CRR derived from UP, as adjustment for UC is considered an important correction for incomplete collections. See [Section 6.6.1](#) for further details.

The definition for the secondary endpoint, major renal response (MRR), specified in the CTP was incomplete. See [Section 5.2](#) for a revision affecting only patients who entered the trial with baseline proteinuria ≥ 3 g/day. There is no change for patients who entered the trial with baseline proteinuria < 3 g/day.

Alternate derivations of PRR & MRR based on UP/UC determined from the 24h urine collections and eGFR calculated from serum creatinine are also added with this version of the TSAP. As with CRR, the alternate PRR & MRR derivations will be analyzed and presented using the same format as used for derivations using UP.

A second alternate derivation of CRR is based on UP/UC as determined from the spot urines and eGFR calculated from serum creatinine. This allows defining CRR based on the samples collected at Weeks 1, 2, 4, 6, 8, 12, 16, 21, 26, 30, 35, 40, 46 and 52. For comparison to the derivations based on the 24h samples, observed proportions at Weeks 26 and 52 were tabulated and pairwise comparisons of each dose to placebo were performed.

Important Protocol Deviations (iPDs) and populations for analysis were updated to reflect learnings and input from Key Opinion Leaders (KOLs).

The logistic regression model specified in the CTP included one of the two stratification variables used at randomization as a covariate, namely race (Asian/non-Asian). The other stratification variable used for the randomization was proteinuria at screening. Proteinuria at screening $<3\text{g/day}$ or $\geq 3\text{g/day}$ (respectively $\text{UP/UC} < 3$ or $\text{UP/UC} \geq 3$) was added to the model as a covariate via the TSAP.

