5. ENDPOINT

5.1 PRIMARY ENDPOINT

The primary endpoint is the proportion of patients with CRR at week 52, where CRR is defined as:

UP<0.5 g/d at week 52

and either

eGFR within normal range at week 52

or

decrease in eGFR<20% from baseline at week 52 if eGFR is below normal range (i.e., below Lower Limit of Normal, where LLN =90 ml/min)

For the assessment of proteinuria for the primary and secondary endpoints, 24h urine collection was performed at baseline, 26 and 52 weeks. Collection was performed in duplicate (2 times 24h collection). The value of proteinuria is the average of the two values. Blinded review of the volumes of the 24h collections and durations of collection raised concern that some collections may have been incomplete. It was decided that the 24h samples should be $\geq 500\text{mL/day}$ and at least 19.5 hours (approximately 80% of 24 hours) to be evaluable. With respect to UP, any collections $< 500\text{mL/day}$ or < 19.5 hours were not evaluated.

Rules for deriving UP from 24h urine collections to determine CRR

Protein excretion rates were transferred to BI in units of mg/dL. The following steps were performed to convert to g/day for deriving CRR.

Protein excretion rate (mg/dL) x 1/100 = Protein excretion rate (mg/ml)

Protein excretion rate (mg/ml) x 24-hour total volume (ml) = UP (mg)

UP (mg) * 1/1000= UP (g/day)

After the interim analysis the team had concerns around how well the thresholds ($\geq 500\text{mL/day}$ and at least 19.5 hours) set for evaluability compensated for incomplete 24h collections. Another method to account for incomplete 24h collections was introduced and CRR was also derived based on the ratio of urine protein/urine creatinine (UP/UC) determined from the 24h collections. As the total amount of creatinine excreted daily in the urine is quite stable, UC is used to stabilize the estimate of proteinuria and is generally accepted as a correction for incomplete collections. With this version of the TSAP, this alternate derivation is incorporated. CRR derived using the UP/UC determination will be analysed and presented using the same methods/format used for CRR derived from UP. There is no change to the eGFR component of the definition; it will be calculated from serum creatinine as defined in the CTP.

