Another alternate derivation of CRR is to base it on UP/UC as determined from the spot urines (and eGFR calculated from serum creatinine.) This allows defining CRR based on the samples collected at Weeks 1, 2, 4, 6, 8, 12, 16, 21, 26, 30, 35, 40, 46 and 52. For comparison to the derivations based on the 24h samples, observed proportions at Weeks 26 and 52 were tabulated and pairwise comparisons of each dose to placebo were performed.

Proprietary confidential information © 2020 Boehringer Ingelheim International GmbH or one or more of its affiliated companies

One of the KOLs consulted, suggested an assessment of how the eGFR threshold for patients below the lower limit of normal (LLN) affected determination of CRR. The suggestion was to allow less of a decrease (10%) in eGFR for those patients below the lower limit of normal (LLN) to achieve CRR compared to the protocol-allowed decrease of 20%.

Rules for imputing missing data or data that was not evaluable are provided in [Section 6.6.1](#). Also specified in Section 6.6.1 are rules for defining CRR for patients who discontinued study medication and/or participation in the trial.

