6.6 HANDLING OF MISSING DATA AND OUTLIERS

6.6.1 Primary and secondary endpoints

As CRR is defined based on UP (and UP/UC) from the two 24h urine collections and eGFR calculated from serum creatinine, rules for derivation of CRR when one or both of the urine samples and/or the serum sample is missing are specified below.

If one 24h urine collection is missing at any time point, then calculations should be based on the available 24h collection at that time point. If one 24h urine collection at any time point is suspected to be incomplete (<500mL/day or time of collection is <19.5 hours) or otherwise not evaluable, then calculations should be based on the unaffected collection at that time point.

Note that the restrictions on volume and duration of collection do not apply to the UP/UC derivation as the adjustment using UC is thought to compensate for incomplete collections.

If both 24h urine collections at baseline are missing, suspected to be incomplete or not evaluable, then UP/UC from the spot urine at baseline should be used to impute baseline UP (or UP/UC) from a 24h collection.

Handling missing data for patients who do not prematurely stop trial medication

If a patient does not have 24h urine collections at week 26 or at week 52, then UP from a 24h collection will be imputed as follows:

- For the week 26 UP, use the mean of UP/UC from the spot urines at weeks 21 and 26
- For the week 52 UP, use the mean of UP/UC from the spot urines at weeks 46 and 52

UP/UC from two weeks are used to get a more stable estimate of UP as it is generally accepted that estimates from the spot urines are not as reliable as estimates from the 24h collections.

For the derivation of CRR using UP/UC from the 24h collection, averages of the two weeks as described above will also be used to impute missing UP/UC from the 24h collection.

For the derivation of CRR using UP/UC from the spot urine, the imputation would be as follows: If UP/UC from the spot urine is missing at week 26, then use week 21. If UP/UC from the spot is missing at 52; use 46.

If no serum creatinine value (to determine eGFR) is available at baseline, then it will be imputed using the value at the screening visit. If no serum creatinine value is available at week 26 or week 52 then it will be imputed using the value at week 21 or week 46, respectively.

For secondary endpoints based on proteinuria and eGFR, the same imputation rules will be applied to derive response at weeks 26 and 52.

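### Does putting both the UP and the UP/UC version of week-52 complete renal response through the primary MCP-Mod analysis break the 20% error limit?

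*SAP*

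**What the plan says.** Protocol 5.2 defines complete renal response (CRR) by urine protein in g/day plus an eGFR condition. SAP 5.1 repeats this for the primary endpoint: "UP<0.5 g/d at week 52", with the eGFR condition.

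SAP 5.1 then reports a measurement worry: "After the interim analysis the team had concerns around how well the thresholds" for volume and duration dealt with incomplete collections. SAP 4 accordingly states that "an alternate derivation of CRR is added with this version of the TSAP". This version uses the protein/creatinine ratio (UP/UC) from the same 24-hour collections and is to be handled with the same methods as UP. SAP 7.4.1 carries that through: "CRR at week 52 (derived using UP and derived using UP/UC from the 24h urine collections) will be analysed using a logistic regression model". The treatment estimates and their covariance matrix then go into MCP-Mod.

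A third version, from spot urine, gets less: "observed proportions at Weeks 26 and 52 were tabulated and pairwise comparisons of each dose to placebo were performed".

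On error control, protocol 7.2 speaks of "protecting the overall probability of type I error of 20" percent, and protocol 7.3.1 describes the evaluation of several dose-response shapes "while keeping full control of the type I error", with a one-sided global level. Protocol 7.2 also calls the trial exploratory, with no formal testing.

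**The concern.** The heading of SAP 7.4.1 promises one primary analysis, yet its text runs two versions of the endpoint through it. It does not say which one establishes a non-flat dose response or what follows if they disagree. Table 6.3:1 marks CRR at week 52 as primary without naming a derivation. The spot-urine version is visibly ranked lower, while the 24-hour UP/UC version is not.

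The two versions can differ. The 500 mL and 19.5 hour limits remove collections from the UP version only; SAP 6.6.1 says: "Note that the restrictions on volume and duration of collection do not apply to the UP/UC derivation".

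The MCP test also acts as a gate: under protocol 7.3.1, models are refitted and a target dose sought only if the test is significant. If success on either version opened the gate, the 20% limit would not hold. Because UP/UC was added after the interim, a reader might also suspect that the more favourable version could be chosen later.

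**Working it through.** **1. Inputs**

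- One-sided global level 20% (protocol 7.3.1).
- 120 patients allocated 40:20:20:40, Expected A rates 0.25, 0.30, 0.38, 0.44, required benefit 10 points, stated success probability 82% (protocol 7.7).
- Assumptions, because the documents do not give them: the parameters of the candidate shapes, and the agreement between the two classifications.

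**2. The plan's own figure**

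MCP-Mod was simulated for a single endpoint: optimal contrasts on the logit scale, refit with AIC averaging, success meaning significance and a modelled benefit of at least 10 points. There were 4,000 trials per scenario.

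| Scenario | Stated | Three assumed shape sets |
|---|---|---|
| Expected A | 82% | 82.7%, 83.3%, 80.9% |
| Shift | 80% | 80.3%, 80.7%, 79.6% |
| Bad | 49% | 49.0%, 49.6%, 48.5% |

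So the protocol's figures are those of one endpoint tested once. On an exactly flat 25% curve, the MCP test was significant in 19.0% to 19.5% of trials, in line with the 20% level.

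**3. Which version decides, from the text**

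| Place | UP in g/day | UP/UC from 24-hour urine |
|---|---|---|
| Protocol 5.2 | defines CRR | not used |
| SAP 4 | basis of the protocol endpoint | alternate derivation |
| SAP 5.1 | defines the primary endpoint | added, same methods |
| SAP 7.4.1 | in the model | in the model |

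Only UP meets the definition of the primary endpoint. Analysing another version in the same way does not redefine that endpoint. With UP deciding, the error is P(Z_UP > c) = 20%, whatever the UP/UC result.

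**4. Error under an either-version rule, which no passage states**

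For two statistics with correlation r, each tested at one-sided 20% (z = 0.8416):

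error = 1 − Φ₂(0.8416, 0.8416; r)

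At r = 0 this is 1 − 0.8² = 36%; at r = 1 it is 20%. If both versions have a 25% response rate, r equals kappa, and the expected number of patients classified differently is 120 × 2 × 0.25 × 0.75 × (1 − kappa) = 45 × (1 − kappa).

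| Kappa (assumed) | Discordant of 120 | Formula | Max-contrast test, 1,000,000 draws |
|---|---|---|---|
| 0.98 | 0.9 | 22.2% | 22.3–22.4% |
| 0.95 | 2.25 | 23.5% | 23.6–23.8% |
| 0.9 | 4.5 | 25.0% | 25.1–25.3% |
| 0.8 | 9 | 27.1% | 27.2–27.5% |
| 0.7 | 13.5 | 28.7% | 28.9–29.2% |
| 0.6 | 18 | not run | 30.2–30.5% |

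The last column spans four assumed shape sets. Simulating the logistic model with the two SAP covariates (assumed prevalences and effects, 20,000 trials) gave 23.1–24.3% at kappa 0.95, 24.9–25.8% at 0.9 and 29.5–31.6% at 0.6.

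**5. How often the two tests would disagree**

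Under Expected A, the two MCP tests reach different verdicts in 6–7% of trials at kappa 0.95, 9–10% at 0.9 and 15–17% at 0.7.

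**6. Where agreement is likely to lie**

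Both versions use the same week-52 collections and the same eGFR. If one collection fails the limits, UP uses the other. If both 24-hour collections are absent, both versions are imputed from the same mean of the week 46 and week 52 spot values (SAP 6.6.1). Discontinuation for lack of efficacy, or before 46 weeks, makes a patient a non-responder on both. This favours high agreement but does not establish a value.

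**The case for a change.** The strongest opposing case is that the SAP itself gives reasons to doubt UP. It questions whether the evaluability limits worked, treats the creatinine adjustment as a worthwhile correction, and places UP/UC in 7.4.1, not in the sensitivity section 7.4.2. After a split result, a reader could cite the SAP for either side. Calling the trial exploratory does not fully answer this, because the protocol also promises a controlled 20% level and makes the test a gate to dose finding. A written ranking would cost a sentence.

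Part of this stands. The public text contains no sentence on how to read a disagreement, and by the simulation above a split would not be rare if agreement were only moderate.

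The rest is weaker. The ranking follows from the definition of the primary endpoint and from the label given to UP/UC. SAP 7.4.2 appears only as a heading in the public text, and Section 9.1, to which 7.4.1 refers for detail of the MCP-Mod stage, is not there at all. Either could hold the rule, so it cannot be counted as missing from the plan. The recorded reason for adding UP/UC is incomplete collection, a concern first raised in a blinded review; nothing shows that those who added it had seen results by arm. If UP decides, the timing of the addition does not affect the primary error rate. Target-dose choice also draws on safety information (protocol 7.3.1), so neither test settles it mechanically.

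**Conclusion.** No change follows. Protocol 5.2 and SAP 5.1 attach the one-sided 20% test and the 10-point criterion to the UP-based response, and on that reading the error stays at 20% and the stated 82% success probability is unaffected. The UP/UC analysis is a parallel check on a known measurement problem, and an analyst would report it as such, discussing any disagreement openly.

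The excess error is hypothetical: about 22% to 25% for kappa 0.98 to 0.9, and about 30% at 0.6, and only if success on either version were accepted. Those figures rest on assumed agreement, equal response rates for the two versions and assumed candidate shapes. A confirming sentence would be harmless, but it would record a ranking the definitions already give and would alter no analysis or result. The sponsor, having argued for the creatinine adjustment, could also reasonably prefer to interpret the two together in an exploratory trial.
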